#### **6.3.5 Adverse events based on signs and symptoms**

All AEs spontaneously reported by the subject or care provider or reported in response to the open question from the study personnel: 'Have you had any health problems since the previous visit/you were last asked?', or revealed by observation will be collected and recorded in the eCRF. When collecting AEs, the recording of diagnoses is preferred (when possible) to recording a list of signs and symptoms. However, if a diagnosis is known and there are other signs or symptoms that are not generally part of the diagnosis, the diagnosis and each sign or symptom will be recorded separately.

#### **6.3.6 Adverse events based on examinations and tests**

The results from protocol mandated laboratory tests and vital signs will be summarised in the clinical study report (CSR). Deterioration as compared to baseline in protocol-mandated laboratory values, vital signs and other safety variables should therefore only be reported as

AEs if they fulfil any of the SAE criteria or are the reason for discontinuation of treatment with the IP.

If deterioration in a laboratory value/vital sign is associated with clinical signs and symptoms, the sign or symptom will be reported as an AE and the associated laboratory result/vital sign will be considered as additional information. Wherever possible the reporting investigator uses the clinical, rather than the laboratory term (e.g., anaemia versus low haemoglobin value). In the absence of clinical signs or symptoms, clinically relevant deteriorations in non-mandated parameters should be reported as AE(s).

Any new or aggravated clinically relevant abnormal medical finding at a physical examination as compared with the baseline assessment will be reported as an AE.

For instructions how to handle AE based on ECG see section 5.2.3 and safety analyses for ECG recording see section 8.5.7.

### **6.3.7 Hypoglycaemia**

Subjects will be asked to test their blood glucose if they experience symptoms suggestive of hypoglycaemia and to record specific symptoms and glucose values in the subject diary.

Study site personnel must obtain accurate information for the subject's file and for the hypoglycaemia page of the eCRF.

Hypoglycemia episodes will be classified in the CSR according to 2018 ADA Criteria as follows (ADA 2018).

#### **Severe hypoglycaemia:**

An event requiring assistance of another person to actively administer carbohydrate, glucagon, or other resuscitative actions. These episodes may be associated with sufficient neuroglycopenia to induce seizure or coma. Glycaemia level may not be available during such an event, but neurological recovery attributable to the restoration of blood glucose to normal is considered sufficient evidence that the event was induced by a low blood glucose concentration.

In summary, hypoglycaemia event will be considered as severe hypoglycaemia if it meets all of the following criteria:

- Require third party assistance
- Prompt recovery after carbohydrate or glucagon administration
- Include symptoms of neuroglycopenia (such as dizziness, confusion, lethargy, headache, visual disturbances, difficulty concentrating, speech difficulty, somnolence/prolonged sleep etc.)

- Glycaemia level, if available, of less than or equal to 70 mg/dL (3.9 mmol/L)

**Clinically significant hypoglycaemia:** Glycaemia level < 54 mg/dL (3.0 mmol/L).

**Hypoglycemia alert value:** Glycaemia level  $\leq$  70 mg/dL (3.9 mmol/L)

Since the glycaemic threshold for activation of glucagon and epinephrine secretion as glucose levels decline is normally 65 to 70mg/dL (3.6 to 3.9mmol/L) and since antecedent blood glucose concentrations of less than or equal to 70mg/dL (3.9mmol/L) reduce sympathoadrenal responses to subsequent hypoglycaemia, this hypoglycaemia alert value of  $\leq$  70 mg/dL (3.9 mmol/L) can be important for therapeutic dose adjustment of glucose-lowering drugs.

If any episodes of probable symptomatic hypoglycaemia (episodes for which symptoms of hypoglycaemia are not accompanied by a blood glucose determination, but which were presumably caused by a blood glucose concentration less than or equal to 70 mg/dL [3.9 mmol/L]) are reported by subjects, the investigator should evaluate and properly record as such in the subject's source records and follow them according to clinical practice. But this category of hypoglycaemia is not considered as clinically significant and will be not recorded in eCRF or reported in CSR.

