### **3.9.2 Discontinuation guideline due to hypoglycaemic events**

Subjects will be recommended to continue on the study and not discontinue from treatment based on single episodes of hypoglycaemia or symptoms of hypoglycaemia unless clinically indicated. The assessment of a single finger stick or central laboratory glucose value should not be the sole assessment used to determine subject discontinuation due to hypoglycaemia.

Clinical indications for discontinuation due to hypoglycaemia may include the following:

Multiple occasions of episodes outlined below that, in the opinion of the investigator, indicate that continued treatment with study therapy is not in the best interest of the subject. This includes, but is not limited to:

- Multiple symptomatic episodes of hypoglycaemia (e.g., sweating, shakiness, increased heart rate (HR), confusion, dizziness, light-headedness, or hunger) in the absence of

environmental factors known to contribute to hypoglycaemia (i.e., excess physical activity, concurrent illness, or missed or delayed meal)

OR

- More than 1 episode of severe hypoglycaemia as defined by the ADA. (See Section 6.3.7 for ADA definition of severe hypoglycaemia.)

Down titration of blinded IP and/or background antihyperglycemic agent will not be allowed at any time during the study.

If finger stick glucose values are discordant from glycaemia control assessed by the central laboratory or with clinical symptoms, the subject's glucose meter should be tested and the procedure for using it reviewed with the subject.

Section 5.2.5.1 provides additional guidance on management and reporting of hypoglycaemia.

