**Table 4 - Hypoglycaemia classes**

Severe hypoglycaemia:	
An event requiring assistance of another person to actively administer carbohydrate, glucagon, or other resuscitative actions.
 
A hypoglycaemia event will be considered as severe hypoglycaemia if it meets all of the following criteria:
 
 
• Require third party assistance
 
• Prompt recovery after carbohydrate or glucagon administration
 
• Include symptoms of neuroglycopenia (such as dizziness, confusion, lethargy, headache, visual disturbances, difficulty concentrating, speech difficulty, somnolence/prolonged sleep etc.)
 
• Glycaemia level, if available, of less than or equal to 70 mg/dL (3.9 mmol/L)
 

Clinically significant hypoglycaemia:	Glycaemia level < 54 mg/dL (3.0 mmol/L)
Hypoglycaemia alert value	Glycaemia level $\leq 70$ mg/dL (3.9 mmol/L)

Number and percentage of subjects who had any hypoglycaemic event and total number of events by treatment group will be presented for the safety analysis set.

A summary of proportion of subjects having severe hypoglycaemia, clinically significant hypoglycaemia, and hypoglycaemia alert value as categorised by the ADA criteria above will also be presented for the safety analysis set. All incidences of hypoglycaemic events and their ADA categorisation will be listed.

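### Severe hypoglycaemia has two definitions under the ADA label, and the working rule can class assisted events as non-severe

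*Protocol*

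**What the plan says.** Protocol 6.3.7 names its standard: "Hypoglycemia episodes will be classified in the CSR according to 2018 ADA Criteria as follows". It then defines a severe event as "An event requiring assistance of another person to actively administer carbohydrate, glucagon, or other resuscitative actions". Two qualifying sentences follow. On neuroglycopenia: "These episodes may be associated with sufficient neuroglycopenia to induce seizure or coma". On events without a glucose value: "neurological recovery attributable to the restoration of blood glucose to normal is considered sufficient evidence" that low glucose was the cause.

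The section then offers a summary, under which a "hypoglycaemia event will be considered as severe hypoglycaemia if it meets all of the following criteria". Four items are listed:

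1. "Require third party assistance".
2. Quick recovery once carbohydrate or glucagon has been given.
3. Symptoms of neuroglycopenia, with an open-ended list of examples.
4. Glucose of 70 mg/dL (3.9 mmol/L) or lower, if a value is available.

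SAP Table 4, introduced as the ADA classification, repeats the one-sentence definition and then the same four items: "A hypoglycaemia event will be considered as severe hypoglycaemia if it meets all of the following criteria". It leaves out the two qualifying sentences. The other two classes in both documents rest on a glucose value alone: below 54 mg/dL, and 70 mg/dL or below.

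Protocol 3.9.2 lists, among possible indications for stopping treatment, "More than 1 episode of severe hypoglycaemia as defined by the ADA" and refers the reader to 6.3.7 for that definition.

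**The concern.** A summary should restate a definition, but this one narrows it. The stated definition turns on assistance; the working rule makes two further features compulsory. Neither document calls the rule a deliberate departure or says which text governs. A programmer working from SAP Table 4 would most naturally implement the explicit list, so the output would carry the ADA label while applying a narrower rule than the definition quoted under that label.

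Hypoglycaemia is an adverse event of special interest, and an episode goes on the adverse event page only if it meets the criteria for a serious event (Protocol 5.2.5.1, SAP 4.2.5.1). For an assisted but non-serious episode, the ADA class is therefore the main place where its severity would show.

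**Working it through.** The plan gives no event rate for severe hypoglycaemia, so there is no figure to reproduce. The check compares the two texts and then enumerates how the rule treats assisted events.

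**Step 1: the texts side by side**

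| Element | Stated definition (Protocol 6.3.7) | Working rule (Protocol 6.3.7, SAP Table 4) |
|---|---|---|
| Assistance of another person | Required, and enough | Required |
| Neuroglycopenia | Possible | Required |
| Recovery | Evidence of cause when no glucose value exists | Required, and must be quick |
| Means of treatment | Carbohydrate, glucagon or other resuscitative action | Recovery must follow carbohydrate or glucagon |
| Glucose | Value may be missing; no threshold | 70 mg/dL or below, if available |

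The restriction that matters comes from items 2 and 3. Item 4 binds only when a value exists, so an event without one faces three mandatory items.

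**Step 2: enumeration**

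Take an event with third-party assistance. Cross quick recovery after carbohydrate or glucagon (yes, no), neuroglycopenic symptoms recorded (yes, no) and glucose (70 mg/dL or below, above 70 mg/dL, no value): 2 × 2 × 3 = 12 combinations. An event treated only by other resuscitative means counts as a no on the first factor.

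- Working rule: severe = quick recovery AND symptoms AND (glucose at or below 70 OR no value).
- Stated definition, read literally: severe = assistance, so every combination.
- Stated definition with the existing glucose condition kept: severe = glucose at or below 70 OR no value.

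| Glucose | Combinations | Stated definition, literal | Working rule | Stated definition plus glucose condition |
|---|---|---|---|---|
| ≤ 70 mg/dL | 4 | 4 | 1 | 4 |
| No value | 4 | 4 | 1 | 4 |
| > 70 mg/dL | 4 | 4 | 0 | 0 |
| Total | 12 | 12 | 2 | 8 |

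The texts disagree on 8 − 2 = 6 combinations even with the glucose condition kept: three with confirmed low glucose and three with no value. These are counts of logical combinations, not frequencies of events.

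**Step 3: where the six go**

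- Confirmed low glucose (three): they drop to one of the two glucose-based classes, although help was needed.
- No value (three): they fit no class in Table 4, because both remaining classes need a glucose value.

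**Step 4: what else would show these events**

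- If serious, they enter all adverse event and serious adverse event summaries (SAP 4.2.5.1). Deaths are also listed and narrated (SAP 4.2.5.2).
- If captured on the hypoglycaemia eCRF page, they are counted among all hypoglycaemic events and listed with their class (SAP 4.2.5.1, Hypoglycaemic Events).
- That condition matters for non-serious events without a glucose value. Protocol 6.3.7 keeps probable symptomatic episodes, defined by symptoms without a glucose measurement, out of the eCRF and the study report. The documents do not say that an assisted episode should be handled that way, but they do not exclude it.

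**The case against.** The strongest reply is that nothing is hidden. The four items are the same in protocol and SAP, are fixed in advance and apply equally to blinded arms. No formal test is made on safety data (Protocol 8.5.7, SAP 4.2.5.1). The list of neuroglycopenic symptoms is broad enough that a typical assisted event should meet it. All of this stands, and it limits the consequence. It does not explain why a narrower rule carries the label of the definition it narrows.

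Two stronger readings are tempting, and the documents support neither.

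- A reader might infer that the rule removes the worst events, such as fatal or non-recovering ones, from the reported safety data. It does not. It changes a class label; the outputs in Step 4 still show serious events, deaths and all captured hypoglycaemic events.
- A reader might infer that 3.9.2 applies a separate ADA standard that conflicts with the classification. It points to 6.3.7, so the only ambiguity is the one inside 6.3.7. Its list is also non-exhaustive and left to the investigator's opinion.

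A further fair objection is that classifying on assistance alone would count an assisted episode with measured glucose above 70 mg/dL, which may not be hypoglycaemia at all. That stands, and it is why the fix keeps the glucose condition.

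Finally, after early termination SAP 6 limits the analyses to those in SAP 4.4. That list keeps hypoglycaemia in the overall adverse event summary but does not name the ADA-category table. This lowers the urgency; the contradiction in the plan remains.

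**Conclusion.** The point holds as an inconsistency of definition. Protocol 6.3.7 and SAP Table 4 each contain two definitions of severe hypoglycaemia under one label, and the narrower one can class assisted events as non-severe: those with slow or no recovery, those treated by other resuscitative means, and those with no recorded neuroglycopenic symptom. Without a glucose value such events have no class.

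The size cannot be estimated. A reader might want to state a percentage, but that needs an assumed count. If an arm had one or two severe events, relabelling one would change the count by 1/1 = 100% or 1/2 = 50%; with none, the figure is undefined. The documents give neither the count nor the share of assisted events that lack an item, so a claim of material under-reporting is not supported.

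No power, sample size or type I error is affected. The conclusion rests on the definition as the protocol writes it out, not on any outside source, and on the assumption that the explicit list is what would be programmed.

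**What to change.** In SAP Table 4, tabulate as severe any event that meets the stated definition (third-party assistance), keeping the existing condition that glucose, if available, is 70 mg/dL or below. Show the count meeting all four items as a supplementary row. If the narrower rule is what the sponsor intends, say so and stop labelling it ADA.

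The sponsor must reconcile the two texts in Protocol 6.3.7. Because 3.9.2 refers to that section, any rewording also reaches the guideline on stopping treatment; no view is taken here on which text should govern that.

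The cost is wording in the SAP and protocol and one table row. The reported severe count could rise. If the ADA-category table is not produced under the reduced analysis list, only the wording changes.

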### **6.3.8 Hy's Law-Not Applicable**

### **6.4 Reporting of serious adverse events**

All SAEs have to be reported, whether or not considered causally related to the IP, or to the study procedure(s). All SAEs will be recorded in the eCRF.

If any SAE occurs in the course of the study, then investigators or other site personnel inform the appropriate AstraZeneca representatives within one day i.e., immediately but **no later than 24 hours** of when he or she becomes aware of it.

The designated AstraZeneca representative works with the investigator to ensure that all the necessary information is provided to the AstraZeneca Patient Safety data entry site **within 1 calendar day** of initial receipt for fatal and life-threatening events **and within 5 calendar days** of initial receipt for all other SAEs.

For fatal or life-threatening AEs where important or relevant information is missing, active follow-up is undertaken immediately. Investigators or other site personnel inform AstraZeneca representatives of any follow-up information on a previously reported SAE within one calendar day i.e., immediately but **no later than 24 hours** of when he or she becomes aware of it.

Once the investigators or other site personnel indicate an AE is serious in the WBDC system, an automated email alert is sent to the designated AstraZeneca representative.

If the WBDC system is not available, then the investigator or other study site personnel reports a SAE to the appropriate AstraZeneca representative by telephone.

The AstraZeneca representative will advise the investigator/study site personnel how to proceed.

## **6.5 Overdose**

Overdose is defined as the accidental or intentional ingestion of any dose of study medication provided by Sponsor that is considered both excessive and medically important. For the purpose of this study, an overdose is defined as a dose of dapagliflozin or saxagliptin in excess of that specified in the CSP (i.e., take more than 1 tablet per day for any of dapagliflozin or its placebo to match or saxagliptin).

For other non-IP (metformin or rescue therapy), overdose will not be collected unless overdose in those medications associated with SAE.

If an overdose is suspected, monitoring of vital functions as well as treatment as appropriate should be performed:

- An overdose with associated AEs is recorded as the AE diagnosis/symptoms on the relevant AE modules in the eCRF and on the Overdose eCRF module.
- An overdose without associated symptoms is only reported on the Overdose eCRF module.

If an overdose on an AstraZeneca study medication occurs in the course of the study, then the investigator or other site personnel inform appropriate AstraZeneca representatives immediately, or no later than 24 hours of when he or she becomes aware of it.

The designated AstraZeneca representative works with the investigator to ensure that all relevant information is provided to the AstraZeneca Patient Safety data entry site.

For overdoses associated with a SAE, the standard reporting timelines apply, see Section 6.4. For other overdoses, reporting must occur within 30 days.

In the event of an overdose, appropriate supportive treatment should be initiated as dictated by the subject's clinical status. Saxagliptin and its active metabolite are removed by hemodialysis (23% of dose over 4 hours). The removal of dapagliflozin by hemodialysis has not been studied.

## **6.6 Pregnancy**

All pregnancies and outcomes of pregnancy should be reported to AstraZeneca.

### **6.6.1 Maternal exposure**

If a subject becomes pregnant during the course of the study, IP should be discontinued immediately.

Pregnancy itself is not regarded as an AE unless there is a suspicion that the IP under study may have interfered with the effectiveness of a contraceptive medication. Congenital abnormalities/birth defects and spontaneous miscarriages should be reported and handled as SAEs. Elective abortions without complications should not be handled as AEs. The outcome of all pregnancies (spontaneous miscarriage, elective termination, ectopic pregnancy, normal birth or congenital abnormality) should be followed up and documented even if the subject was discontinued from the study.

If any pregnancy occurs in the course of the study, then the investigator or other site personnel informs the appropriate AstraZeneca representatives within 1 day i.e., immediately but no later than 24 hours of when he or she becomes aware of it.

The designated AstraZeneca representative works with the investigator to ensure that all relevant information is provided to the AstraZeneca Patient Safety data entry site within 1 or 5 calendar days for SAEs (see Section 6.4) and within 30 days for all other pregnancies.

The same timelines apply when outcome information is available.

The PREGREP module in the CRF is used to report the pregnancy and the PREGOUT is used to report the outcome of the pregnancy.

#### **6.6.2 Paternal exposure**

There is no restriction on fathering children or donating sperm during the study.

#### **6.7 Medication error**

For the purposes of this clinical study a medication error is an unintended failure or mistake in the treatment process for saxagliptin or dapagliflozin that either causes harm to the subject or has the potential to cause harm to the subject.

A medication error is not lack of efficacy of the drug, but rather a human or process related failure while the drug is in control of the study site staff or subject.

Medication error includes situations where an error

- Occurred
- Was identified and intercepted before the subject received the drug
- Did not occur, but circumstances were recognized that could have led to an error

Examples of events to be reported in clinical studies as medication errors:

- Drug name confusion
- Dispensing error e.g. medication prepared incorrectly, even if it was not actually given to the subject

- Drug not administered as indicated, for example, wrong route or wrong site of administration
- Drug not taken as indicated e.g. tablet dissolved in water when it should be taken as a solid tablet
- Drug not stored as instructed e.g. kept in the fridge when it should be at room temperature
- Wrong subject received the medication (excluding IxRS errors)
- Wrong drug administered to subject (excluding IxRS errors)

Examples of events that **do not** require reporting as medication errors in clinical studies:

- Errors related to or resulting from IxRS - including those which lead to one of the above listed events that would otherwise have been a medication error
- Subject accidentally missed drug dose(s) e.g. forgot to take medication
- Accidental overdose (will be captured as an overdose)
- Subject failed to return unused medication or empty packaging
- Errors related to background and rescue medication, or standard of care medication in open label studies, even if an AstraZeneca product

Medication errors are not regarded as AEs but AEs may occur as a consequence of the medication error.

If a medication error occurs in the course of the study, then the investigator or other site personnel informs the appropriate AstraZeneca representatives within 1 day i.e., immediately but **no later than 24 hours** of when he or she becomes aware of it.

The designated AstraZeneca representative works with the investigator to ensure that all relevant information is completed within 1 (Initial Fatal/Life-Threatening or follow up Fatal/Life-Threatening) or 5 (other serious initial and follow up) calendar days if there is an SAE associated with the medication error (see Section 6.4) and within 30 days for all other medication errors.

